## List of acronyms

Acronym	Description
AAL	Ambient Assisted Living
MCI	Mild Cognitive Impairment
SMCI	Senior with Mild Cognitive Impairment
IC	Informal Caregiver
FC	Formal Caregiver

### **Executive summary**

To generate a qualitative product for the market, international projects such as engAGE require extensive and accurate evaluations on the use and usability of the platform, composed of four main parts: a social robot, a tablet application, an activity tracker, and a machine learning algorithm that analyses data coming from the first three components. In the first instance, a lab test will then be conducted to improve all related interfaces by ensuring that the features and the design globally match the end users' needs. The aim of those assessments is to reduce risks and to maximize the system's benefits and market fit, as an improving tool regarding the cognitive decline of older people with mild cognitive impairment and a viable solution regarding carer's workload and treatment pressure.

To appraise the strength of adhesion, but also to rank the system's strengths and weaknesses, a field trial will be set up in order to introduce and install engAGE platform in the natural environment of older people with mild cognitive impairment that need assistance and physical and cognitive stimulation. The field trial will then take place at both the healthcare organization and older people's home and will allow us to check back if the ideas, concepts, clickable mock-ups and prototype are satisfactorily designed and if there are still elements left to be improved to satisfy the client's needs.

Evaluations' outcomes will conduct, step by step, to the final product development, taking also risks, and significant social or ethical issues into account. All evaluations are therefore endowed with ethical values and principles that are indispensable for the smooth running of the project.

## **1** Introduction

The engAGE platform co-design has been based on the requirements identified in the previous set of interviews with end users: older people with mild cognitive impairment (MCI) and (in)formal caregivers (IC and FC).

A whole set of different evaluations have then been considered, to progressively check if the produced elements of engAGE meet the global expectations and needs of the end users. Assessments' iterations on the prototypes created are then necessary to know whether the improvements gradually made are indeed responding to the needs and requirements identified earlier. On this purpose, two tests will be run: the **engAGE 1st integrated prototype** will be evaluated in the lab testing, whereas the **2nd engAGE integrated prototype** will be evaluated in the lab testing, whereas the **2nd engAGE integrated prototype** will be evaluated in the lab testing.

The focus of this deliverable is to explain in broad terms all the required evaluations during the **lab test** and the **field trial**, and to provide information about participants' recruitment, methodology and measurements.

#### 1.1 Objectives

The objectives of the engAGE project are to counteract and slow down cognitive decline progression, to enhance the intrinsic capacity of the users, and to support the wellbeing of older persons with mild cognitive impairment (MCI) by providing an ecosystem of services based on an innovative system that integrates social robots, IoT-based monitoring, and machine learning techniques.

engAGE targets the following challenges and needs for the main end-user groups: older people with MCI, informal caregivers (family caregivers), and formal caregivers (healthcare professionals).

The project is primarily focused on **older people with MCI**, aiming to improve their quality of life and well-being, allowing them to preserve their identity, to reduce stress, memory loss, or communication challenges. The social robot can be a great tool in engaging older adults in this kind of activities. It is always available and able to provide verbal clues or suggestions according to older adult's wishes, needs and memories. Moreover, the social robots may coach the older adults to perform daily activities with greater independence (i.e. coaching stepwise prompting to complete activities inhome) and support to caregivers as well.

Since caring for people with MCI puts a significant burden on **informal caregivers**, having the support of a technological platform can reduce anxiety, worries, and stress. The caregivers can personalize the content of interventions to the wishes and preferences of the older adults. Together with the older adults, they can be involved with the robot in joyful and fun activities like drama playing, storytelling, etc.

The **formal caregivers** who need to keep track of older adult progress which is a difficult and timeconsuming process due to the lack of objective monitoring of cognitive decline and wellbeing may get valuable support from the cognitive assessment procedure implemented by the ML algorithm. Also, the social robot and tablet may facilitate the follow-up of older adults through reminders and cognitive interventions.

For the purpose of engAGE, the following end-users will be involved in two rounds of experimentation (a lab test and a field trial), as follows:

Older adults			Secondary end users (informal caregivers)			Secondary (centres)				
Italy	Switzerland	Norway	Italy	Switzerland	Norway	Italy	Switzerland	Norway		
5	5	5	5	5	5	1	1	1		

#### Table 1. Participants for lab test

#### Table 2. Participants for field trials

Prima	ary end user	s (SMCI)	Secor	ndary end users ( caregivers)	informal	Secondary (centres)	Control group		
Italy	Switzerland	Norway	Italy	Switzerland	Norway	All pilot sites			
20- 22	20-23	8-10	20-22	20-23	8-10	≥2	≥30 (≥10 per each pilot site)		

#### 1.2 Overview of the platform

In this section, an overlook of the platform is presented to the reader. The engAGE system will offer four main services built around a social robot for self-managing and sustaining the cognitive function of older adults with MCI: (i) holistic monitoring of daily life activities and perceived health state and wellbeing (Monitoring, Self-Reporting and Big Data Processing Service - MSRBD), (ii) assessment of cognitive state and potential decline by leveraging on machine learning (ML) algorithms (ML-based Cognitive Decline Assessment Service - MLCDA),(iii) personalized cognitive function support and coaching using drama or storytelling and social robots as main tools (Social Robot Coaching and Cognitive Stimulation - SRCCS) and support, communication and personalization for end-users (Communication Platform and Intelligent Personalization - CPIP). The following figure (Fig. 1) schematizes the engAGE platform that integrates social robots, IoT-based monitoring, and machine learning techniques.

Figure 1. Engage platform architecture

The primary end users will interact with 3 devices: the Pepper robot, a tablet, and an activity tracker through three services dashboards:

- MSRBD service: the Tellu platform allows the collection of data from sensor device through a
  mobile app that pushes the data to MLCDA. It will feature an Android app to be used by the
  end-users as gateway of data collection process. Parameters such as heart rate, sleep status,
  activities, etc. are monitored and will be further used by the MLCDA service as input for ML
  algorithms.
- CPIP service MEMAS application can be considered as the hub of the whole system for providing the dashboards for end-user interactions. It will be a web application with several dashboards in which all the end user categories can communicate through MEMAS which shows the results of the ML analysis, and allows the personalization of the services. Also, CPIP will help collecting self-assessment data through questionnaires and make this data available to MLCDA service that will fuse it with the rest of the monitored data and use it as input for ML algorithms.
- SRCCS service: The Android version of Pepper's tablet offers personalized games and activities to the user through an easy-to-use interface. The games will be also integrated into MEMAS to allow the user to play at home. The games results will be made available to MLCDA service to be further processed and fused into the ML process.

The informal caregivers can set reminders and, more in general, an agenda for the cared senior through the MEMAS application. Thus, the senior can use the tablet to fulfil other activities such as listening to the music, watching photos, and so on.

The formal caregivers supervise the execution of activities by the SMCI and help them when needed.

#### 1.3 Dashboards

In this section, the single dashboards that compose the platform are described in detail.

1.3.1 MEMAS

The MEMAS system is a Life Mastering Assistant or a cognitive aid that is suitable for people with MCI.

The MEMAS system contains functionality which will help people e.g., with MCI:

- Calendar with reminders
- Step by step instructions for daily activities in form of series of images with spoken comments or videos
- Entertainment functions
- Photos with spoken comments and videos
- Music
- Easy access to radio channels
- Easy access to network newspapers
- Cognitive games
- Training exercises
- Weather forecasts
- Self-reporting questioners
- Very simple to operate video communication system
- Display the results from the ML algorithms for the secondary end-users

The MEMAS system is usable by both primary and secondary users. The primary user is the person with MCI who physically owns a device with a MEMAS client, and who uses MEMAS as an aid to organize their everyday life. Secondary users are relatives and others in the support system around the primary user, who assist with this in various ways. A primary user can be connected to several secondary users. A secondary user can assist several primary users. In the administration module (a website page), the secondary user can manage an activity calendar, build albums with photos and videos, configure access to favourite radio channels and newspapers etc. As the cognitive state of the person with MCI deteriorates, the secondary user may remove some of the MEMAS functionality from the primary user's device. In general, the secondary user can edit the primary user's interface in order to make the use of MEMAS as simpler as possible, and tailored to the primary user's needs.

#### 1.3.2 Pepper

Pepper is a humanoid social robot able to dialogue with the user by speaking, moving, and expressing emotions. Pepper is also equipped with an Android tablet placed at its chest. The user logs through the tablet at every session, then it interacts with the robot and play the planned activities (drama play, cognitive games, physical games). In order to track the user's progress, each performance is recorded and scores are sent to the cloud along with the user ID.

Once the type of game is selected, the SMCI will be redirected to a new screen in which all the games corresponding to the type selected will be displayed. As a result of the co-creation phase and requirements specification (D2.1 and D2.2) we have identified different categories of cognitive games that can be implemented for older adults with MCI:

- "Familiar games" (5 different games): crossword, karaoke, memory card, sudoku, and find 7 differences game.
- "Quizzes" (3 different games): a picture quiz, a musical quiz or a cultural quiz.
- "Physical games" (3 different games): miming, dancing and yoga.
- "Story/play telling" (2 different games): story listening or plays/poems reciting.

The games will be iteratively developed and included in the platform in the different versions of the prototype while considering end-users' feedback.

When the SMCI is playing and succeeding a task, the robot will congratulate with him/her. To be sure that the SMCI will understand what the robot says, the words are displayed on the screen like subtitles. Alternatively, the robot makes a sound or vibrates when the SMCI put wrong answers to signal SMCI that the system is involved in the game they are playing. However, SMCI can also choose to have a robot which won't react to false answers, as some will maybe find it childish or demotivating.

#### 1.3.3 Mobile application gateway

The Monitoring, Self-Reporting and Big Data Processing service has little user interaction outside of the use of sensor devices. This service features a mobile application gateway which transfers data from sensor devices and into the cloud (see D2.2 Section 4.1.1). In the first iteration, it will transfer Fitbit data from the Fitbit service. It does so automatically while running in the background on the mobile device (Android tablet) of the primary user. There will be a one-time initiation where the user needs to authenticate with both TelluCare and the Fitbit service. Thereafter the user does not normally need to interact with the app, but it needs a user interface to show status and allow turning data transfer off and/or logging out of accounts.

The app and its usage are described in D1.1, section 5.1.4. Once the login and Fitbit authentication has been established, the app will run in the background, regularly polling data from the Fitbit service. The user will be notified with an Android notification if there is an error with the data transfer. The app user interface has a status field to indicate the current status. This is colour-coded green/yellow/red, but any issue/error is also communicated with text.

## 2 Lab Test

#### 2.1 Procedure

engAGE 1st integrated prototype will be tested and evaluated in a lab setting. The aim of the test is to assess the usability of the prototype, the user experience, the perceived usefulness, and integration of everyday activities. To this purpose, 30 end users (15 older users and 15 FC/IC) will be recruited over the 3 test sites. Before arrival, all participants will receive information about the engAGE project and they will be asked to complete a brief questionnaire providing demographic, health and wellbeing state, and technology-related data. Moreover, participants will be informed on the collection, storage, and privacy management of their data (the participants will sign an informed consent). In a controlled setting, all volunteers will be trained so that they will be aware of how to use the engAGE ICT solutions and how to interact with the social robot. The following methods are going to be applied: (i) mock-ups will deliver fast feedback about main navigation and rough design of the services interfaces, (ii) the solutions will be used in controlled environments to test the re-used solution effectiveness for the defined main use cases to determine improvements and adaptation if needed and (iii) initial prototypes will be tested with usability methods, combining questionnaires, thinking aloud and observations. The end-user partners will set up focus group sessions to define/refine the scenarios and personas. The focus groups will receive a short training, with explicitly designed material (flyers, training videos, devices, etc.), giving a complete overview of the aims of the study and its tasks.

- **Recruitment phase (R)**: the recruitment protocol will include demographic information on the subjects, as well as information about their health status and cognitive condition. The information will be collected with the help of the caregiver/family member if needed.
- **Baseline evaluation (T0)**: it will consist of collecting information about wellbeing state and technology-related data, in order to understand the needs and the technological literacy of the end users.
- **Feedback (T1)**: at the end of the test the end users will answer structured questionnaires on usability and provide general impressions on the prototype. Moreover, problems occurred during the testing and experienced difficulties will be reported.

#### 2.2 Inclusion and exclusion criteria

In this section, the inclusion and exclusion criteria for involving end users in engAGE lab test are described.

#### 2.2.1 Inclusion criteria

- PRIMARY END USERS:
  - over 65 years old;
  - o self-reported initial memory loss.
- SECONDARY END USERS (INFORMAL CAREGIVERS):
  - Over 18 years old;
  - Primary informal caregiver of people with memory loss.
- TERTIARY END USERS (FORMAL CAREGIVERS):
  - Over 1 year experience;
  - Psychologist, neurologist, occupational therapist, nurses from health care facilities or paid by the participants.

#### 2.3 Channels of recruitment

To ensure that the right participants are included in the evaluations, each partner must have its own recruitment technique, and ensure that the inclusion criteria mentioned above are met. Several channels are available for this purpose and everyone is free to proceed in the easiest perceived way.

#### 2.3.1 Italy (INRCA)

Regarding the recruitment channel, Italian partners will use the contact list of their neurology unit and Alzheimer day-care centre to communicate with potential participants of previous projects and initiatives, as well as with other people who might be interested in contributing to the project evaluations. This method makes possible to be in contact with clients met before and with whom a relationship of trust has been already established.

#### 2.3.2 Switzerland (HUG)

Swiss partners will contact the different units of the HUG in neurology, the memory center and the day care center in Geneva. They will be contacted to know if they are interested to participate in the development of the project by introducing us to potential participants to evaluate the project.

#### 2.3.3 Norway (KARDE)

Norwegian partners will recruit participants through day care centres in Arendal municipality as well as other people who might be interested in contributing to the project evaluations, and who are known to Karde from previous AAL-projects. Some recruitment may also be conducted through Karde's social media accounts and by announcements on the project's web page on karde.no.

#### 2.4 Scales and tools

Table 3. Protocol of questionnaires on Lab test for older people with MCI

PROTOCOL of QUESTIONNAIRES for OLDER USER	R	то	T1
Socio-demographics checklist	Х		
Technology literacy		Х	
System Usability Scale (SUS)			х
Semi-structured questionnaire on usability, acceptance, willingness to pay			х

Table 4. Protocol of questionnaires on Lab test for informal and formal caregivers

PROTOCOL of QUESTIONNAIRES for IC/FC	R	то	T1
Socio-demographics checklist	х		
Technology literacy		Х	

 System Usability Scale (SUS)
 X

 Semi-structured interview on acceptance, usability, willingness to pay, quality of work
 X

The quantitative tools are all standardized, and they are:

The **System Usability Scale (SUS)** [9] is a reliable tool for measuring usability. It consists of a 10-item questionnaire with five response options for respondents, from 'Strongly agree' to 'Strongly disagree'. It allows for evaluation of a wide variety of products and services, including hardware, software, mobile devices, websites and applications. It is easy to administer to participants and can be used on small sample sizes with reliable results and can effectively differentiate between usable and unusable systems.

Finally, a **semi-structured Interview** to evaluate the formal/informal caregivers' perspective on acceptability, usability and demand & cost information is built ad hoc, as the interview for the SMCI on willingness to pay and problems and/or suggestions about the prototype functionalities (see Annex).

#### 2.5 Description of the testing

In this section, the testing is descripted in detail.

The tests will take place in a controlled environment in each pilot site:

- Italy (INRCA): Youse Lab (Laboratory of technology usability) inside INRCA hospital;
- Switzerland (HUG): EvaLab (Laboratory of technology usability) inside HUG hospital;
- Norway (KARDE): Partly in Karde's premises and partly at day care centres in Arendal.

At the controlled environment, the older user interacts with the social robot and the tablet and is supervised by the relative informal caregiver, by one researcher (at least) and one technical assistant.

The interaction will consist in practicing the following activities in this order:

- Introduction to the project and explanation (by researcher)
- wearing activity tracker and use the dialogue app (log in and sharing data);
- free dialogue with the robot;
- cognitive game with the robot Crossword;
- physical game with the robot Miming game;
- do one task on MEMAS (search for photo, creating account).

This interaction is planned to last about 1 hour. Before the interaction the end user (and his/her informal caregiver) will answer the questionnaires (T0). During the interaction every problem occurred or any suggestion provide by end users will be annotated and reported in the final report along with questionnaires asked after the test (T1).

## 3 Field trial

#### 3.1 Study design

The field trial will be conducted as a controlled longitudinal study, with a before and after design where the observations are made on a series of enrolled individuals, receiving the intervention described below with control group, with data collected before and after the installation and use of the technical solution. The goal of trial evaluation is to assess the engAGE technology integration into everyday life, effectiveness on mitigating the cognitive decline, acceptance over six months, security and reliability of proposed solutions as well as the business perspective reflecting the market demand (including the willingness to pay) for the developed services. The field trial procedure will be divided into two different phases, after the recruitment of the participants: Baseline evaluation (T0, M1) and Final evaluation (T1, M6), with the aim of collecting data as follows:

- **Recruitment phase** (R): the recruitment protocol will include general information on the subjects, in particular, health status and cognitive condition. The information will be collected with the help of the caregiver/family member if needed.
- **Baseline evaluation** (T0, M1): that will consist of the first real contact with the users and their families, before the start of the field trial.
- **Mid-term evaluation** (T1, M3): the aim of mid-term evaluation is to collect useful information on the use of the engAGE platform after a short period of use for detecting and analysing the technology acceptance and usability issues.
- Final evaluation (T2, after six months of use, M6): the aim of this phase is to collect useful information on the whole benefits perceived by the users after a meaningful period of use of the system. The final evaluation will be conducted after the system de-installation, to detect and analyse the impact of the system in the daily life of the older people and their family. Moreover, the final evaluation aims to gain knowledge on elderly technology acceptance and usability issues to be compared with mid-term results (T1), in order to assess the longterm acceptance and provide methodological approach for further studies in the field.

The field trial is a pilot study, that is, a small-scale study, conducted mainly to control whether and how the developed services are perceived useful and usable. The defined qualitative and quantitative key performance indicators (KPI) will be evaluated and used to assess the degree to which engAGE meets the elders' needs, wishes and priorities in all trial sites (i.e. achieving better engagement, better social interaction, and accurate measurement of cognitive decline based on machine learning techniques). The measurements collected from the real-life trials will be elaborated and evaluated, to assess the ecosystem performance and validate the success of the project-developed technologies. The field trial will conduct only a partial evaluation of the effectiveness of services in relation to some dimensions of cognitive status of older people with MCI.

In the following scheme (Fig. 2) the study design is summarized. A certain number of people are recruited for the study, then those who do not meet the criteria or decline the participation are excluded. The remaining participant are randomly assigned to the experimentation group or to the control group. In randomization technique based on a single sequence of random assignments is used. A list of random numbers generated by the computer is used and subject is assigned a number based on their order of inclusion in the study. According to this technique, the 80 subjects are randomly assigned to the

experimentation group or to the control group. Then, for both the groups it has to be taken note of who loose follow up, discontinued intervention, and/or are excluded from analysis.

Figure 2. Field trial - study design

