The **Warwick-Edinburgh Mental Wellbeing Scales (WEMBS)** [12] is used to enable the measuring of mental wellbeing in the general population. The 14-item scale WEMWBS has 5 response categories, summed to provide a single score. The items are all worded positively and cover both feeling and functioning aspects of mental wellbeing, thereby making the concept more accessible. The scale has been widely used nationally and internationally for monitoring, evaluating projects and programmes and investigating the determinants of mental wellbeing.

The **Unified Theory of Acceptance and Use of Technology (UTAUT)** [7] is a 20-item questionnaire that examines the acceptance of technology, determined by the effects of performance expectancy, effort expectancy, social influence and facilitating conditions.

The **Quality of Life – Alzheimer's Disease (QoL-AD)** [13] uses a scale of 1–4 (poor, fair, good, or excellent) to rate a variety of life domains, including the patient's physical health, mood, relationships, activities, and ability to complete tasks.

The **Zarit Burden Interview (ZBI)** is a caregiver self-report measure [9], containing 22 items. Each item on the interview is a statement which the caregiver is asked to endorse using a 5-point scale. Response options range from 0 (Never) to 4 (Nearly Always).

The **System Usability Scale (SUS)** [8] is a reliable tool for measuring usability. It consists of a 10-item questionnaire with five response options for respondents, from 'Strongly agree' to 'Strongly disagree'. It allows for evaluation of a wide variety of products and services, including hardware, software, mobile devices, websites and applications. It is easy to administer to participants and can be used on small sample sizes with reliable results and can effectively differentiate between usable and unusable systems.

Finally, a **semi-structured Interview** to evaluate the formal/informal caregivers' perspective on acceptability, usability and demand & cost information is built ad hoc, as the interview for the SMCI on usability and acceptability.

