#### 3.6 Description of the intervention

In this section, the intervention is descripted in details.

The experimental group (EG) use the engAGE system in two different settings: at healthcare organization and at home. At the healthcare organization, the primary end user (SMCI) interacts with Pepper. The interaction **at healthcare organization** is supervised by tertiary end users (formal caregivers, i.e., occupational therapist, psychologist, nurse, etc...) and includes the following activities: dialoguing with the robot, storytelling, drama play, cognitive and physical games. This interaction is planned to last about **1 hour and to be scheduled twice a week for 6 months**. **At his/her home**, the older user interacts with the tablet and is supervised by the relative informal caregiver. Also in this case, the user plays cognitive and physical games installed on MEMAS app. Even this activity is **performed for 0,5 hour, every day for 6 months**. Throughout the whole period of experimentation (unless (s)he decides otherwise), the older user wears the smartwatch that measures his/her physiological parameters and the steps. Any activity performed by the seniors is assigned by formal caregiver and can be personalized taking into account the user's abilities (difficulty levels of the games), lifestyle (reminding and monitoring services), and social interactions.

The activities performed by the user through the engAGE system are schematized in the figure below:

Figure 3. Summary of engAGE activities

Table 7. Games of the Engage platform

Name of games	Description
	Familiar games

Crossword	Helps with long term memory, having	★: easy level (infinite tips)			
	definition or pictures.	★★: medium level (limited tips)			
Karaoke	Helps SMCI to have fun while singing songs they already know (train memory without noticing).	★★★: hard level (no tips)			
Memory card	Helps with spatial memory, which can help SMCI to find lost objects in the future.				
Sudoku	Helps with visual memory, using numbers instead of letters can be easier and more enjoyable. It's an appreciated game for SMCI.				
2 differences game	Helps to stay focus, observe, retain the information to seek.				
Quizzes					
Picture quiz	Find the celebrities/animals behind.				
	$\star$ : picture $\star$ $\star$ : pixelated photo $\star$ $\star$ $\star$ :	★: silhouette			

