#### UNIFIED THEORY ON ACCEPTANCE AND USABILITY OF TECHNOLOGY (UTAUT)

1.	If I were to use the system, I would be afraid of making mistakes.
2.	If I were to use the system, I would be afraid of breaking something.
3.	The system scares me
4.	The system frightens me
5.	I think it is a good idea to use the system
6.	Using the system would make my life more interesting.
7.	It is good to use the system
8.	I have everything I need to use the system correctly
9.	I know enough about the system to be able to use it correctly
10.	I think I will use the system in the next few days
11.	I am certain that I will use the system in the next few days.
12.	I am planning to use the system in the next few days.
13.	I believe the system can accommodate my needs.
14.	I believe the system will only do what I need it to do at the moment.
15.	I believe the system will help me when I feel it is necessary.
16.	I enjoy that the system communicates with me.

17. I enjoy performing operations with the system.

18. I think the system is fun.
19. I think the system is interesting.
20. I think the system is boring
21. I think I will learn to use the system quickly.
22. I think the system is easy to use.
23. I believe that I can use the system without help.
24. I think I could use the system with someone beside me.
25. I think I could use the system with a manual
26. I think the system is useful for me
27. It would be convenient for me to have the system
28. I believe the system can help me in many activities.
29. I think the staff would be happy if I use the system.
30. I think I would make a good impression if I were to use the system.
31. I think I would believe the system if it gave me a warning
32. I would follow the warnings the system would give me

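### UTAUT items 10–12, and arguably item 8, are not comparable between T1 and T2 because T2 follows removal of the system; the long-term acceptance contrast leans towards a false loss

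*Combined protocol and SAP*

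**What the plan says.** Section 3.1 sets the mid-term evaluation (T1) at month 3, to collect "information on the use of the engAGE platform after a short period of use for detecting and analysing the technology acceptance and usability issues". Section 3.6 has home use "performed for 0,5 hour, every day for 6 months", so at T1 the senior still has the system. For T2, at month 6, section 3.1 states: "The final evaluation will be conducted after the system de-installation". The same paragraph says that T2 findings on acceptance and usability are set against the mid-term ones. The purpose it gives for doing so is "in order to assess the longterm acceptance".

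Table 5 (section 3.5) marks UTAUT and SUS for seniors at both T1 and T2. Section 3.7 analyses both in the experimental group only. Annex 3 prints the UTAUT form in the T2 set. Items 10, 11 and 12 ask whether the senior thinks they will use the system in the coming days, is certain of it, or plans to; item 12 reads "I am planning to use the system in the next few days". Item 8 asks whether the senior has what is needed to use the system properly.

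**The concern.** The T1–T2 contrast is the only comparison the plan names for long-term acceptance. At T1 the system is in the home; at T2 it has been taken away. Any change between them mixes a change of attitude with the fact of removal. Because UTAUT is analysed in the experimental group alone, no concurrent group separates the two.

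On the three intention items the effect of removal has a known direction. They ask about a near future in which the system will normally not be there, so a senior with undiminished acceptance is pushed to a lower answer. Acceptance over six months is one of the trial goals in section 3.1, and the following text describes the pilot as run mainly to see whether the services are perceived as useful and usable. A fall produced by the schedule could be reported as waning acceptance.

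**Working it through.** **1. Is the system present at each time?** T1 is month 3 of six months of daily use, so yes. T2 follows de-installation, and section 4.2 requires the platform to be returned at the end of the trial, so no. The interval between removal and T2 is not given. An opening sentence of section 3.1 labels the final evaluation T1, but the comparison sentence names the mid-term results, so the contrast meant is month 3 against month 6.

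**2. Which items depend on having the system?** Annex 3 prints no separate T1 set, so I assume the same form is used at both times.

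| Content | Depends on possession? | Direction after removal |
|---|---|---|
| UTAUT 10–12, near-term use | Yes | Down |
| UTAUT 8, having what is needed | Arguable | Down, if so read |
| Other UTAUT items (opinion, enjoyment, hypothetical use) | Not shown | Not established |
| SUS (conditional, general or retrospective wording) | Not shown | Not established |

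**3. Does anything in the plan offset this?** I find no month-6 assessment before removal, no instruction to answer retrospectively, no omission of items and no adjustment. Caregivers complete SUS at T2 only (Table 6), so the contrast concerns seniors.

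**4. Size, for illustration only.** The plan gives no figure to reproduce. Assumptions that are not in the documents: items coded 1–5, a total or mean over all 32 items, and the other 29 items unchanged. If k items each fall by d points, the mean falls by k × d / 32. The total has a range of 32 × 4 = 128 points.

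| d on items 10–12 (k = 3) | Fall in total | Fall in mean | Share of range |
|---|---|---|---|
| 1 | 3 | 3/32 = 0.09 | 2.3% |
| 2 | 6 | 6/32 = 0.19 | 4.7% |
| 3 | 9 | 9/32 = 0.28 | 7.0% |

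With item 8 added (k = 4) the falls in the mean are 0.125, 0.25 and 0.375. A subscale of items 10–12 alone would fall by the full d.

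**5. How sensitive a significance statement would be.** Suppose further a paired z-test at two-sided 0.05. The chance of a significant decline from this artefact alone is Φ(fall / (SD/√n) − 1.96). Table 2 gives 20 + 20 + 8 = 48 to 22 + 23 + 10 = 55 seniors with the system. However, 80 randomised (section 3.1) with at least 30 controls leaves at most 50. No allocation ratio is stated, so n = 40 is shown too.

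| d | SD of change | n = 40 | n = 48 | n = 55 |
|---|---|---|---|---|
| 1 | 0.6 | 17% | 19% | 21% |
| 2 | 0.6 | 51% | 58% | 64% |
| 3 | 0.6 | 84% | 90% | 94% |
| 1 | 0.8 | 11% | 13% | 14% |
| 2 | 0.8 | 32% | 37% | 41% |
| 3 | 0.8 | 60% | 68% | 74% |

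The spread, 11% to 94%, comes from the assumptions. It shows that the artefact can matter, not how often it would.

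**The case against.** Four arguments on the other side deserve weight.

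- **The timing is deliberate.** Section 3.1 puts T2 after removal to see the system's impact on daily life. That is a fair reason for the other outcome scales; it does not help a UTAUT comparison with T1.
- **Seniors may answer hypothetically.** Items 1, 2 and 27 are worded for someone who does not have the system, and section 5.1 offers those who want longer use a place in similar studies. Some may therefore still agree with items 10–12. This makes the size of the fall uncertain; it does not make the answers comparable with T1.
- **Giving the form before removal is not enough.** A senior who knows the system is about to go still cannot sincerely plan to use it in the days ahead. This stands, and it is why leaving the items out of the score comes first in the fix.
- **No analysis is specified that would produce a false significant result.** Section 3.7 asks only for an analysis of UTAUT in the experimental group. Section 4.1 defines no UTAUT score and no paired T1–T2 test. This also stands, although a descriptive change in means would carry the same bias.

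A reader might also infer that measured usability must fall. The documents do not support that: no SUS item is shown to depend on possession, and many of the interview questions are in the past tense.

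**Conclusion.** The point holds for UTAUT items 10–12 and arguably for item 8. In experimental-group seniors they are not comparable between T1 and T2, and removal biases them towards a false loss of acceptance. SUS and the remaining UTAUT items may be distorted, but neither presence nor direction is established. Under the assumed coding, the effect on a 32-item mean is modest, 0.09 to 0.28 for a fall of 1 to 3 points; on an intention subscale it would be the whole fall. It would be tempting to say that the schedule will probably yield a significant decline, but that rests on a score, test, response scale, drop and SD that the plan does not give.

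Acceptance is a secondary outcome (section 3.4), and MAC-Q, the primary one, is not touched by this point. A change is still worth making, because the bias is predictable, concerns a stated goal and is cheap to avoid.

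Separately, section 3.5 says that UTAUT "is a 20-item questionnaire that examines the acceptance of technology", while the Annex 3 form has 32 items. The two should be reconciled; the mismatch is not evidence about timing.

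**What to change.** 1. In the T1–T2 comparison, leave UTAUT items 10–12 out of the score and report them separately at each time, stating whether the system was in place. On the 32-item form that leaves 29 items. Repeat without item 8 (28 items) as a sensitivity analysis. State in section 4.1 how the score is formed.
2. Amend section 3.1 so that the month-6 UTAUT and SUS are given at a session already scheduled before de-installation, for example one of the last twice-weekly supervised sessions of section 3.6. Keep the other outcome scales after de-installation as planned. This does not rescue items 10–12, so step 1 is still needed.

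The cost is that one acceptance subscale drops out of the long-term contrast and the T2 questionnaires are split over two existing contacts. No new instrument and no change of sample size is needed.
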